
STATISTICAL CONSIDERATIONS
	
Primary Analysis Subjects will be assessed for radiographic progression as described in Section 8. Time from first dose of ADT to radiographic progression or death, whichever occurs first, will be calculated for each subject. For subjects who discontinue study treatment due to reasons other than death or investigator assessed progression, every effort will be made to continue tumor assessments on schedule until radiographic progressive disease or subject death. Subjects who do not have radiographic progression or death will be censored at their last measure for radiographic progression. The primary hypothesis test will be conducted at a one-sided 0.1 significance level using a stratified log-rank test. Kaplan-Meier methods will be used to report rPFS graphically by arm including the median rPFS and 12 and 24 month rPFS proportions in the ITT population. The log-rank test without stratification will be used as a sensitivity analysis.
 
Secondary analysis Toxicity will be described within each arm by type, maximum grade and frequency among the safety population. The proportion of subjects in each arm with skeletal related events and secondary neoplasms will be reported individually and a mid p-value test will compare the proportions between arms.
 
Time to castration resistance (TTCR), PSA progression free survival (PCWG2 criteria), and Overall Survival (OS) will be reported by arm using Kaplan-Meier methods and tested using the stratified log-rank test. The 2 -year PSA PFS and OS proportions with 90% confidence intervals and median time to castration resistance will be reported using Kaplan-Meier methods. Analyses will be completed on the ITT population.
 
Binomial proportions with 90% binomial confidence intervals of subjects who achieve PSA <math>\leq</math> 0.2 ng/mL at 7 months after treatment initiation will be reported by arm. Similarly, the proportions and associated confidence intervals of subjects who achieve PSA <math>\leq</math> 4 ng/mL at 7 months after treatment initiation will be

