#### 4.1 STRATIFICATION FACTORS

Subjects will be stratified based on serum total alkaline phosphatase at baseline and extent of disease (described below). Randomization will occur within stratification group.

- Extent of Disease: <6 skeletal metastases with no visceral metastases versus  $\geq 6$  skeletal metastases or visceral metastases.
- Serum total alkaline phosphatase at baseline: Normal vs Abnormal. Abnormal alkaline phosphatase is defined as > 130 IU/L.
- Early Induction or Late Induction status will not be a stratification criterion.

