## **12. STATISTICAL CONSIDERATIONS**

### **12.1 Study Design**

Newly diagnosed metastatic prostate cancer subjects with  $\geq 2$  bone metastases will be accrued and randomized 1:2 to ADT without or with Radium-223 dichloride respectively. The primary aim of the study is to determine if the addition of Radium-223 dichloride to ADT will improve efficacy in this prostate cancer population. The primary efficacy endpoint is radiographic progression-free survival (rPFS). We expect the control arm with ADT alone to have a 12 month median rPFS. The addition of radium-223 to ADT will target an improvement of 7 months for a median rPFS of 19 months. A total of 140 events are required for at least 90% power to detect Hazard Ratio of 0.632 with a one-sided alpha of 0.1. The study powering is based on assumptions of 19 months median rPFS in the experimental arm and 12 months median rPFS in the control arm. Assuming exponential time to event data, a yearly dropout rate of 10% with

accrual in 24 months and study duration of 48 months, 204 subjects will provide 90% power with a 10% one-sided type I error. Hypothesis testing for the primary endpoint will be conducted at a one-sided 0.10 significance level using a stratified log-rank test. Randomization of 68 subjects to the ADT arm and 136 subjects to the ADT+R arm will be completed with stratification by extent of disease (<6 skeletal metastases without visceral disease versus  $\geq 6$  skeletal metastases or visceral disease) and baseline alkaline phosphatase (normal versus abnormal), abnormal alkaline phosphatase defined as  $> 130$  IU/L. If time anticipated for the number of events required for analysis significantly exceeds 48 months, the sponsor may enroll additional subjects to reach required number of events.

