### 12.6 Analysis of Primary Objective

Subjects will be assessed for radiographic progression as described in section 8. Time from first dose of ADT to radiographic progression or death, whichever occurs first, will be calculated for each subject. For subjects who discontinue study treatment due to reasons other than death or investigator assessed progression, every effort will be made to continue tumor assessments on schedule until radiographic progressive disease or subject death. Subjects who do not have radiographic progression or death will be censored at their last measure for radiographic progression. The primary hypothesis test will be conducted at a one-sided 0.1 significance level using a stratified log-rank test. Kaplan-Meier methods will be used to report rPFS graphically by arm including the median rPFS and 12 and 24 month rPFS proportions in the ITT population. The log-rank test without stratification will be used as a sensitivity analysis.

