### 12.7 Analysis of Secondary Objectives

Toxicity will be described within each arm by type, maximum grade and frequency among the safety population. The proportion of subjects in each arm with skeletal related events and secondary neoplasms will be reported individually and a mid p-value test will compare the proportions between arms.

Time to castration resistance (TTCR), PSA progression free survival (PCWG2 criteria), and Overall Survival (OS) will be reported by arm using Kaplan-Meier methods and tested using the log-rank test. The –time to castration resistance, the 2-year PSA PFS and OS proportions with 90% confidence intervals will be reported using Kaplan-Meier methods. Analyses will be completed on the ITT population.

Binomial proportions with 90% binomial confidence intervals of subjects who achieve PSA  $\leq$  0.2 ng/mL at 7 months after treatment initiation will be reported by arm. Similarly, the proportions and associated confidence intervals of subjects who achieve PSA  $\leq$  4 ng/mL at 7 months after treatment initiation will be described.

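### The synopsis tests TTCR, PSA-PFS and OS with the stratified log-rank test, while Section 12.7 names the log-rank test without stratification, and nothing says which prevails

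*Combined protocol and SAP*

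**What the plan says.** The two current statements on TTCR, PSA-PFS and OS are:

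- Synopsis, Statistical Considerations: these endpoints "will be reported by arm using Kaplan-Meier methods and tested using the stratified log-rank test".
- Section 12.7: these endpoints "will be reported by arm using Kaplan-Meier methods and tested using the log-rank test".

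For the primary endpoint the synopsis and Section 12.6 agree. Section 12.6 reads "The primary hypothesis test will be conducted at a one-sided 0.1 significance level using a stratified log-rank test" and then "The log-rank test without stratification will be used as a sensitivity analysis".

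On the design, Section 4.1 states "Subjects will be stratified based on serum total alkaline phosphatase at baseline and extent of disease" and "Randomization will occur within stratification group". Section 12.1 repeats the two factors, and the allocation is 1:2.

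No section says whether the synopsis or Section 12 takes precedence. Neither place gives a target hazard ratio, a significance level or a sidedness for the tests of these three endpoints; 12.7 gives only the 90% level of the confidence intervals.

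**The concern.** Two different tests are specified in advance for each of three secondary endpoints, one of them OS. They can give different p-values, and an analyst could later cite either page for the one reported. Fixing the test before the data are examined removes that choice.

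There is also a question of efficiency. Randomizing within strata balances the arms on the stratification factors. If those factors affect outcome, an unstratified log-rank test does not take credit for that balance. Its variance estimate is then too large for the design, so it rejects less often than its nominal level under the null and has less power under the alternative. Read literally, 12.7 would give OS, TTCR and PSA-PFS the test that 12.6 keeps as a sensitivity analysis for rPFS, without giving a reason.

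**Working it through.** **1. Is 12.7 only shorthand?** Section 12.6, immediately before it, uses both terms: the stratified test for the primary analysis, and the test without stratification as the sensitivity analysis. Beside that, an unqualified log-rank test in 12.7 reads most naturally as unstratified. The conflict with the synopsis is therefore real.

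**2. Reproduce the plan's own figure.** The documents size only rPFS. Section 12.1 states "A total of 140 events are required for at least 90% power to detect Hazard Ratio of 0.632 with a one-sided alpha of 0.1". The Schoenfeld formula with a proportion p = 1/3 in the control arm is

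events = (z₀.₉₀ + z₀.₉₀)² / [p(1 − p)(ln HR)²] = (1.2816 + 1.2816)² / [(2/9)(ln HR)²].

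- HR = 12/19: 6.5695 / (0.2222 × 0.21117) = 140.0.
- HR = 0.632: 6.5695 / (0.2222 × 0.21056) = 140.4, rounded up to 141. Power at 140 events is 89.9%.

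Expected events for 68 and 136 subjects were checked with exponential times, medians of 12 and 19 months, uniform accrual over 24 months, 48 months in total and 10% yearly dropout. With λ the event hazard, γ = −ln(0.9)/12 and τ = λ + γ, each subject's event probability is (λ/τ)[1 − (e^(−24τ) − e^(−48τ))/(24τ)]. This gives about 0.780 (control) and 0.640 (experimental), so 68 × 0.780 + 136 × 0.640 ≈ 140.1 events. The sample size reproduces and does not depend on this point.

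**3. Size of the difference between the tests.** The documents do not quantify how prognostic the factors are, so this step rests on assumptions.

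- From Section 12.1 (rPFS values, borrowed for the secondary endpoints): 68 v 136, HR 0.632, one-sided 0.10, and the accrual, duration and dropout above.
- Assumed: two independent factors, each level 50%, with a prognostic HR of 1.0 to 3.0 per factor; hazards centred on a 12-month control median; permuted blocks of 6 within the four strata.
- 20,000 simulated trials per setting. The Monte Carlo standard error of a rejection rate near 0.10 or 0.90 is √(0.1 × 0.9/20,000) = 0.002.

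| Assumed HR, factor 1 / factor 2 | Power, unstratified | Power, stratified | Difference (points) | Type I error, unstratified | Type I error, stratified |
|---|---|---|---|---|---|
| 1.0 / 1.0 | 90.9% | 90.3% | +0.6 | 0.105 | 0.104 |
| 1.5 / 1.5 | 89.6% | 90.3% | −0.7 | 0.099 | 0.105 |
| 2 / 1.5 | 87.6% | 89.7% | −2.1 | 0.094 | 0.106 |
| 2 / 2 | 86.6% | 90.3% | −3.7 | 0.087 | 0.105 |
| 3 / 2 | 83.1% | 89.8% | −6.7 | 0.076 | 0.103 |
| 3 / 3 | 79.7% | 89.5% | −9.8 | 0.069 | 0.106 |

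**4. An OS-like case.** The control median is set to 44 months, the ADT-alone median in the docetaxel trial described in Section 1.5, with HR 0.632 again assumed. At 2/2 there are about 64 events; power is 66.6% v 68.6% and type I error 0.095 v 0.106. At 3/3 (6,000 trials, about 68 events) power is 63.4% v 70.2%.

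**5. Follow-up limited to 24 months.** Section 7.10 follows subjects for two years from randomization. A separate run with that limit (4,000 trials per setting) gives 85.6% v 86.9% at 1.5 per factor, 83.3% v 86.9% at 2.0 and 80.3% v 86.8% at 2.5. The OS-like case, with about 50 events, gives 58.8% v 59.5%, 59.5% v 61.0% and 59.0% v 62.2%. The direction and rough size are the same.

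**6. Is either factor prognostic?** In the docetaxel trial of Section 1.5, median OS on ADT alone was 32.2 months in high-extent patients against 44 months overall. That suggests extent matters, although that trial defined extent differently from the stratum in Section 4.1. Nothing in the documents quantifies the effect of ALP in this population.

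**The case against.** The strongest reply is that this is probably one dropped word with little consequence. The secondary objective in Section 2.2.2 is to estimate proportions and a median. Those Kaplan-Meier estimates and 90% intervals are the same whichever log-rank test is used. None of the three endpoints is powered. Keeping to the unstratified test errs toward missed effects, not false positives. At moderate factor effects the loss is small, and smaller still at OS-like event counts. All of this stands and limits the weight of the point. It does not remove the contradiction, because tests are still planned and two are named.

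A reader might go further than the documents allow in three ways:

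- That 12.7 governs, so the plan has settled on the weaker test. No precedence rule is written, and the synopsis, equally current, already names the stratified test.
- That the factors were chosen because they are prognostic. Sections 4.1 and 12.1 give no reason for the choice, and the evidence on extent is indirect.
- That a substantial power loss is established. The larger losses need two strongly prognostic factors. Every power figure here borrows an HR and alpha set for rPFS, since none is given for these endpoints.

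**Conclusion.** The point holds as an inconsistency that should be corrected. The choice of p-value left open for TTCR, PSA-PFS and OS follows from the text alone and needs no simulation.

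The efficiency argument is conditional. On the assumptions in the working, the unstratified test gives up about 1 to 4 points of power at factor HRs of 1.5 to 2, and about 10 points at 3/3. Its actual type I error falls to about 0.09 at 2/2 and 0.07 at 3/3. In an OS-like case the loss is about 1 to 2 points at 1.5 to 2 and about 7 at 3/3. With non-prognostic strata there is no loss.

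The primary analysis is stratified in both places, so neither it nor the sample size is affected.

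**What to change.** In Section 12.7, insert the word stratified before log-rank for TTCR, PSA-PFS and OS. Name the same two randomization factors as in the primary analysis: extent of disease and baseline ALP. Add the unstratified test as a sensitivity analysis, as 12.6 does for rPFS. This brings 12.7 into line with the synopsis, the primary test and the randomization.

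The same edit should state the significance level and sidedness of these secondary tests; otherwise the p-value is still not fully specified.

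The cost is a sentence or two, with no change to data collection or sample size. The statistical price is about 0.6 points of power (90.3% v 90.9%) if neither factor is prognostic, which is negligible. If the sponsor prefers the unstratified test, the synopsis should be changed to match and the reason given. Either way, the two passages need to agree before the data are examined.

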**Bone Turnover Marker Correlative Study Design:**

Serial serum specimens will be submitted for the proposed correlative studies at the following time points:

- Pre-Dose on Day 1 of Cycle 1 (in the late induction group; for the early induction group, there will be no pre-treatment specimen)
- Thereafter on Day 1 of each Cycle (Cycle 2-Cycle 7) of protocol specified therapy for the following biomarkers: N-telopeptide (NTX), C-collagen fragments (CTX-I EIA), osteocalcin (OC) & bone alkaline phosphatase (BAP).
- At end of treatment visit.

Refer to the CLM for collection, labeling, processing and shipping instruction for the serum samples.

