We will evaluate the distribution of pre-randomization marker levels (ALP and bone markers) among those who have and have not started ADT prior to randomization. If it appears that the prior initiation of ADT impacts the study entry bone marker levels to a fair extent, then all marker analyses will be conducted stratified by ADT initiation status. Descriptive statistics by arm will report the time to ALP progression among all subjects using Kaplan-Meier methods. ALP and serum bone markers will be reported by arm for each time-point using means or medians and corresponding measures of variability for all subjects with serum. Percentage change in ALP from baseline and changes from baseline in bone markers will be calculated for each later time point and tested between arms using a t-test or Wilcoxon rank test. If there is sufficient data, a mixed model will be used to model each endpoint over time to determine if the changes are different between treatment arms. Exploratory analysis will use separate Cox models with rPFS, PSA PFS, TTCR, and OS as the individual outcomes and treatment group, one marker, and the interaction between treatment and marker as independent covariates to find associations with outcomes. These models can be expanded to include other subject factors to determine if the marker contributes to outcome above subject factors that are known to be associated with the outcome. Similarly, logistic models can be used with 7-month PSA outcomes. The model analyses are considered exploratory for this trial. Thus, they are not powered and will not use multiple comparisons adjustments.

Worst pain will be reported from the BPI (SF) at each time point with a mean or median and the associated measure of variability and tested between arms with a t-test or Wilcoxon rank test. Comparisons at the times post-baseline will be compared between treatment arms using a paired test (t-test or Wilcoxon rank test.) WHO will be reported categorically by arm at each time point and tested between arms using the Mantel-Haenszel chi-square test. The change in WHO score from baseline will be calculated and be the outcome in a cumulative logistic model. Treatment arm will be included as an independent covariate to test if the change in pain is different between arms. Each post-baseline measure will be a separate model.

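### The between-arm tests of percentage change in ALP and change in bone markers are valid but ignore the baseline value, and so lose precision that a baseline-adjusted log model would recover

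*Combined protocol and SAP*

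**What the plan says.** Section 12.7, repeated in the synopsis, sets out the marker comparison: "Percentage change in ALP from baseline and changes from baseline in bone markers will be calculated for each later time point". These changes are then "tested between arms using a t-test or Wilcoxon rank test". No rule is given for choosing between the two tests, and no covariate or log scale is named.

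Two further provisions bear on the same data:

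- "If there is sufficient data, a mixed model will be used to model each endpoint over time". The aim is to see whether changes differ between arms. Neither a baseline term nor a transformation is mentioned.
- If earlier ADT appears to have shifted marker levels at study entry, "all marker analyses will be conducted stratified by ADT initiation status". This is the only adjustment foreseen, and it does not use the baseline marker value.

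Section 12.7 also lets models be expanded with other subject factors, but that sentence concerns the Cox models for clinical outcomes.

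Baseline ALP is a randomization factor. Section 4.1 lists "Serum total alkaline phosphatase at baseline: Normal vs Abnormal" and adds that "Abnormal alkaline phosphatase is defined as > 130 IU/L". For the bone markers, section 9.1 says that "for the early induction group, there will be no pre-treatment specimen", and that samples are stored until funding for the assays is secured.

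**The concern.** A change score gives the baseline value a fixed weight, whatever its real correlation with follow-up. Unless that correlation is very high, this over-corrects and leaves avoidable variance in the treatment contrast. A regression on baseline estimates the weight from the data. Percentage change adds a second difficulty: for a right-skewed marker it is itself right-skewed, which costs a t-test further power.

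Section 1.6 treats ALP as one of the readouts of whether radium-223 acts on bone disease, and there are only 68 controls. At stake is the precision of a supporting comparison, and whether it yields an effect estimate with an interval that could help plan the later phase 3 trials that section 1.6 has in mind. A rank-test p-value alone does not give one.

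**Working it through.** **The plan's own figures.** The documents give no power, SD, correlation, effect size or significance level for any marker comparison. The only sizing is for rPFS in section 12.1. It reproduces: (1.2816 + 1.2816)² / [(2/9) × (ln 0.632)²] = 140.4 events against the stated 140. It has no bearing on ALP beyond supplying the arm sizes, 68 and 136.

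**Assumptions, none from the documents.** Log-normal ALP with log-SD σ = 0.7 at both times; a treatment effect of −0.25 on the log scale, a ratio of exp(−0.25) = 0.78 or 22% lower ALP; baseline/follow-up correlation ρ of 0.4, 0.6 or 0.8; two-sided 0.05; both values available for all 204 subjects.

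**Variance on the log scale.**

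- Change score: 2(1 − ρ)σ².
- Baseline-adjusted: (1 − ρ²)σ².
- Ratio, adjusted to change: (1 + ρ)/2, which is 0.70, 0.80 and 0.90 at the three correlations.

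**Closed-form check.** The standard error is the relevant SD × √(1/68 + 1/136) = SD × 0.1485, and power ≈ Φ(0.25/SE − 1.96).

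| ρ | SD, log change | Power | SD, adjusted | Power |
|---|---|---|---|---|
| 0.4 | 0.767 | 59% | 0.642 | 75% |
| 0.6 | 0.626 | 77% | 0.560 | 85% |
| 0.8 | 0.443 | 97% | 0.420 | 98% |

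**Simulation of the tests the plan allows.** The adjusted model here contains only arm and log baseline.

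| ρ | t-test, % change | Wilcoxon, % change | Adjusted log model | Gain over Wilcoxon | Gain over t-test |
|---|---|---|---|---|---|
| 0.4 | 50% | 56% | 73% | 17 | 23 |
| 0.6 | 70% | 74% | 84% | 10 | 14 |
| 0.8 | 95% | 96% | 98% | 2 | 3 |

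The adjusted column agrees with the closed form to within about two points.

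**Sensitivity to the assumed SD.** A second set of simulations sized the effect so that a t-test on log change would have 80% power, with log-SD 0.4 to 1.0 and ρ 0.5 to 0.8. Power was 62.5% to 79.0% for the t-test on percentage change, 76.6% to 78.6% for Wilcoxon and 82.8% to 89.6% for the adjusted log model. The t-test was worst in the most skewed setting (log-SD 1.0, ρ 0.5), at 62.5% against 89.2%.

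**Sensitivity to the level.** If an effect gives the log-change test 80% power at one-sided 0.10, the adjusted model has 91.2%, 87.9%, 84.6% and 83.1% at ρ 0.3, 0.5, 0.7 and 0.8.

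**Validity.** With no treatment effect (log-SD 0.7, ρ 0.7), every method rejected in about 5% of simulated trials.

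**The case against.** The case against acting has four parts, and much of it stands.

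- **Wilcoxon is permitted.** Percentage change and log ratio have the same ranks, so Wilcoxon on percentage change is not harmed by skewness. A reader might infer that the plan commits itself to a badly skewed outcome. It does so only if the t-test is chosen, and the fair comparator for the size of the loss is Wilcoxon. A gap of 17 and 10 points remains at the lower correlations.
- **A mixed model is foreseen.** ALP is measured every cycle through Cycle 12 and every 12 weeks afterwards, so the data condition is likely to be met for ALP. Such a model could use the baseline information, but the text does not say whether baseline enters as a response, as a covariate or not at all. The plan is under-specified here; it does not rule adjustment out.
- **The target is secondary at most.** Objective 2.2.3 and section 8.11 name ALP normalization and time to ALP progression, not percentage change. The plan also says that "The model analyses are considered exploratory for this trial. Thus, they are not powered". No stated operating characteristic is therefore wrong.
- **The bone markers are different.** A reader might infer that unused baseline information is on hand for every marker. That holds fully only for ALP. Early induction subjects have no pre-treatment bone-marker specimen, and the assays are unfunded.

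A reader might also infer that the unadjusted tests are biased. They are not: randomization keeps them valid.

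**Conclusion.** The point holds as one of efficiency. The planned between-arm test of ALP change is valid but less precise than a baseline-adjusted analysis of the same data. Under the assumed SD of 0.7 and a 22% reduction, the adjusted log model gains about 2 to 17 points of power over Wilcoxon, and up to 23 over the t-test. The gain shrinks as the correlation rises and is slight at 0.8. The documents do not give the correlation, SD, effect or level, so these figures show a range and do not predict the result.

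The figures are for percentage change in ALP. They do not carry over exactly to the bone markers, which are compared on plain change. The rPFS analysis and its conclusion are untouched. The change is worth making because it costs almost nothing and gives an interpretable estimate.

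**What to change.** In section 12.7 and the synopsis:

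1. Make the main between-arm ALP comparison a linear model at each time point, or the mixed model already planned, of log ALP on arm, log baseline ALP, the two stratification factors and ADT-initiation status. Report the geometric mean ratio with its interval.
2. Keep Wilcoxon on percentage change as a sensitivity analysis and drop the open choice between t-test and Wilcoxon.
3. If the mixed model is used, remove its dependence on sufficient data for ALP and state how baseline enters. State its status too, since the section calls model analyses exploratory.
4. State which ALP value is the baseline for early induction subjects, because section 7.1 accepts either a pre-ADT value from records or one taken before Cycle 2 Day 1 treatment.
5. Use the same model for the exploratory bone markers if they are assayed, and name the pre-radium sample that serves as baseline. The pre-dose Cycle 2 Day 1 sample is one candidate, since it is scheduled in both induction groups.

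The cost is SAP wording. No new data are needed, and trial conduct does not change.

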### **2.2 Secondary Objectives**

2.2.1 Assess safety and toxicity including incidence of skeletal related events (SRE) and secondary neoplasms.

2.2.2 Estimate the proportion of subjects with  $PSA \leq 0.2$  ng/mL after 7 months of androgen deprivation therapy, the proportion of subjects with  $PSA \leq 4$  ng/mL after 7 months of androgen deprivation therapy, the median time to castration resistance, 2-year PSA progression free survival proportion (PCWG2 criteria) and 2-year overall survival proportion in both arms.

2.2.3 Determine the proportion of subjects with elevated serum total alkaline phosphatase (ALP) at baseline who normalize their alkaline phosphatase after 12 weeks of therapy, assess time to ALP progression ( $\geq 25\%$  increase in ALP from baseline/nadir (whichever is lower) and above ULN), association of ALP x in both arms.

2.2.4 Evaluate change in pain level and analgesic use using the Brief Pain Inventory (BPI short form) and WHO ladder scale, respectively, with therapy.

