### 5 TREATMENT PLAN

#### 5.1 Treatment schedule

Subjects will be randomized in a 2:1 ratio in favor of the experimental arm to one of the following treatments:

- Arm A (Control): LHRH agonist/antagonist + bicalutamide
- Arm B (Experimental): LHRH agonist/antagonist + bicalutamide + radium-223 dichloride

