### **9.4 Assessment of Pain Level and Analgesic Use**

A key finding in the randomized phase III ALSYMPCA trial was the reduction in pain with radium-223 dichloride therapy. In the present study, subject-reported pain will be collected using standard paper surveys during clinic visits. Pain will be assessed by means of the Brief Pain Inventory Short Form (BPI-SF) questionnaire at baseline, on Cycle 4 Day 1 visit before dose and at the end of treatment visit. The worst pain recorded at each time point will be used as a numeric score for quantitative comparison across time points and between treatment arms. Analgesic use scores will be assigned by the treating physician according to the World Health Organization (WHO) scale at baseline, on Cycle 4 Day 1 visit before dose and at the end of treatment visit.

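### The paired test specified for BPI worst pain cannot compare independent arms of 68 and 136, so change in pain from baseline has no valid between-arm test

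*Combined protocol and SAP*

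**What the plan says.** Objective 2.2.4 is "Evaluate change in pain level and analgesic use using the Brief Pain Inventory (BPI short form") and the WHO ladder. Section 9.4 says that worst pain at each time point will be "used as a numeric score for quantitative comparison across time points and between treatment arms".

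Section 12.7 gives worst pain two sentences, repeated in the synopsis:

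- The first has the score summarised at each time point with "the associated measure of variability and tested between arms with a t-test or Wilcoxon rank test". This is an ordinary two-sample comparison of raw scores.
- The second reads "Comparisons at the times post-baseline will be compared between treatment arms using a paired test (t-test or Wilcoxon rank test".

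For the neighbouring endpoints, section 12.7 handles change explicitly. For markers, "changes from baseline in bone markers will be calculated for each later time point and tested between arms", and ALP is treated the same way as percentage change. For analgesic use, "The change in WHO score from baseline will be calculated and be the outcome in a cumulative logistic model", with treatment arm as covariate.

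On the design, section 5.1 states "Subjects will be randomized in a 2:1 ratio in favor of the experimental arm", and section 12.1 gives "Randomization of 68 subjects to the ADT arm and 136 subjects to the ADT+R arm". Section 4.1 randomizes individual subjects within strata and leaves induction group out of the stratification. No matching is described anywhere.

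**The concern.** The second sentence names a test that does not fit the design, and it is the only candidate in the plan for an analysis of BPI change. The mixed model in section 12.7 sits in the marker text and is not stated to cover pain. The WHO model concerns analgesic use.

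The analyst would therefore have to choose among a two-sample test on change, a baseline-adjusted test and separate paired tests within each arm, possibly after seeing the data. The last of these is the risky choice. It describes change with therapy but does not compare treatments, and with 2:1 allocation the larger arm reaches significance more easily for the same true change. Section 13.4 requires results of all secondary objectives to be posted, so the choice would be visible.

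Two further points affect the pain analysis:

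- **Baseline.** It is Cycle 1 Day 1, before ADT, for late-induction subjects, but Cycle 2 Day 1, after ADT has started, for early-induction subjects. Section 12.7 provides for this difference with markers but not with pain.
- **Last assessment.** The third pain visit is not named consistently.

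**Working it through.** **Inputs.** Arms of 68 and 136, 90% power and one-sided 0.10 come from section 12.1, where power and alpha are stated for the primary endpoint only. The documents give no SD, baseline correlation or alpha for pain. Assumed here: complete forms, equal SD in both arms, the same alpha and power as the primary test, and correlation ρ of 0.3, 0.5 or 0.7.

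**The plan's own figures.** 204 × 1/3 = 68 and 204 × 2/3 = 136. The primary event count is (1.2816 + 1.2816)² / [(1/3)(2/3)(ln 0.632)²] = 140.4, against 140 stated. These reproduce; the plan has no corresponding figure for pain.

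**Can the stated test be run?** No. Paired t and signed-rank routines given 68 and 136 values stop because the lengths differ. Forcing one-to-one pairs uses at most 68 of the 136 ADT+R subjects:

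- SE with 68 pairs = √(2/68) = 0.171 SD; two-sample SE = √(1/68 + 1/136) = 0.1485 SD. Relative efficiency = (1/68 + 1/136)/(2/68) = 75%.
- The result depends on the arbitrary pairing. In one simulated data set with no true difference, p ran from 0.006 to 1.0 over 2,000 pairings; the two-sample p was 0.29.

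**If read as paired tests within each arm.** Suppose both arms truly change by the same amount d (ρ = 0.5, so the change has SD 1; two-sided 0.05). The chance of significance in an arm of size n is Φ(d√n − 1.96).

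| Common change d | 68-subject arm | 136-subject arm | ADT+R significant, ADT not |
|---|---|---|---|
| 0.2 SD | 0.378 | 0.645 | 0.645 × (1 − 0.378) = 0.40 |
| 0.3 SD | 0.696 | 0.938 | 0.938 × (1 − 0.696) = 0.28 |
| 0.5 SD | 0.985 | 1.000 | about 0.015 |

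For a common change of 0.2 to 0.3 SD, an apparent radium effect on pain would therefore arise in 28% to 40% of trials with no difference between arms.

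**Valid alternatives.** Raw-score detectable difference = (1.2816 + 1.2816) × 0.1485 = 0.381 SD. ANCOVA multiplies this by √(1 − ρ²), and a change score by √(2(1 − ρ)). Power at a true 0.381 SD is Φ(0.381/(0.1485 × factor) − 1.2816).

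| ρ | Detectable: raw | ANCOVA | Change | Power: raw | ANCOVA | Change |
|---|---|---|---|---|---|---|
| 0.3 | 0.381 | 0.363 | 0.450 | 90% | 92.0% | 81.2% |
| 0.5 | 0.381 | 0.330 | 0.381 | 90% | 95.3% | 90.0% |
| 0.7 | 0.381 | 0.272 | 0.295 | 90% | 98.9% | 97.9% |

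The raw-score test alone gives up 2 to 9 points of power against ANCOVA. The choice between change score and ANCOVA moves power by 11, 5 or 1 points.

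**Simulation check.** 4,000 trials; ρ = 0.5; half the subjects early induction with baseline 0.5 SD lower (assumed).

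| Analysis | Rejection under the null | Power at 0.381 SD |
|---|---|---|
| ANCOVA with induction group | 9.3% | 95.0% |
| Wilcoxon on change | 9.8% | 87.7% |
| Raw t-test | 9.8% | 89.6% |

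**Effect of the mixed baseline on the arm comparison.** Two halves differing by 0.5 SD add 0.5²/4 = 0.0625 to a change variance of 1. The change-score detectable difference then rises only to 0.381 × √1.0625 = 0.392 SD.

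**Third pain visit, side by side.**

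- The study calendar, its footnote 7 and section 7.5: Cycle 8 Day 1.
- Sections 9.4 and 9.5: end of treatment.
- WHO ladder text in section 9.5: end of study visit.
- Section 7.10: the end-of-treatment test list contains no pain survey.
- Section 8.2.2 describes the first imaging assessment as the end of protocol therapy. The calendar's first post-baseline imaging is at Cycle 8 Day 1, so the conflict may be mainly one of naming, but the text does not say so.

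**The case against.** The strongest reply is that this is compressed drafting with little consequence. Section 9.4 wants two comparisons, and the sentence may run together a paired one within arms and an unpaired one between arms. Objective 2.2.4 speaks of change with therapy and does not itself ask for a between-arm test of change. Under randomization, the raw-score test in the preceding sentence estimates the same treatment difference as a test on change, and at ρ of 0.5 or below the change test is no more powerful. ANCOVA is then a preference, and a 0–10 score may pile up at zero because eligibility admits men without pain.

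Much of this stands. A valid between-arm test of pain level exists, the intent was probably sensible, and the mixed baseline hardly affects the arm comparison. The power figures rest on assumed inputs and rank alternatives; they do not measure harm already done.

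It does not rescue the sentence, which specifies an analysis that cannot be run and leaves the reader to guess its replacement. Nor does a floor at zero remove the case for baseline adjustment. With ρ = 0.5 and about 57% zeros at baseline (assumed), power was 80% for the raw t-test, 83% for ANCOVA and 66% for Wilcoxon on change. With about 75% zeros it was 70%, 74% and 54%. ANCOVA's gain shrinks to 3 to 4 points but remains. The change test loses clearly, which is a reason not to make it the main analysis.

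**Conclusion.** The concern holds. As written, the paired between-arm test cannot be carried out, and BPI change from baseline has neither a valid between-arm test nor a baseline-adjusted one. Objective 2.2.4 is not left without any between-arm analysis, since raw worst pain and WHO change both have one.

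The loss from relying on the raw-score test alone is modest: 2 to 9 points of power against ANCOVA over ρ of 0.3 to 0.7, assuming complete forms, one-sided 0.10 and roughly normal scores, and 3 to 4 points under the assumed floors at ρ = 0.5. The larger risk is that the sentence is carried out as separate within-arm tests and read as a treatment comparison.

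This should be corrected before analysis. It concerns a secondary endpoint with no stated power; the primary test and sample size are untouched. The naming of the third pain visit is a separate inconsistency that also needs resolving.

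**What to change.** In section 12.7 and the synopsis, replace the paired-test sentence with wording such as:

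> Worst pain at each post-baseline assessment will be compared between arms by ANCOVA with treatment, baseline worst pain, the two randomization strata (extent of disease, baseline ALP) and induction group. This is the main between-arm pain comparison. The raw-score test is supportive, and a two-sample Wilcoxon test on change from baseline is a sensitivity analysis. Any paired test is limited to within-arm change from baseline, reported by induction group, and no treatment comparison is drawn from it.

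The minimum repair is to apply the plan's bone-marker approach to BPI: change from baseline at each later time point, tested between arms by a two-sample t-test or Wilcoxon rank-sum test.

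Separately, reconcile the third pain assessment in sections 9.4 and 9.5 (including the WHO ladder text) with the calendar, footnote 7 and section 7.5, and name that visit in section 12.7.

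The cost is wording in section 12.7, the synopsis and section 9. No data collection is added if the visit already in the calendar is the one retained.
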